6.1.4 RANDOMIZATION

Following the completion of the baseline assessment, the site PC will review the consent, document the randomization block variables (gender, medication, past suicide attempt), obtain randomization assignment from the Data Center at Duke University, and reveal randomization results to an already assigned counselor. Note that student participants will learn of their treatment assignment by the counselor at their first treatment visit (this procedure was used in the pilot project and received very favorably by students and counselors).

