9.2 CAMPUS TRIAL SAMPLE SIZE DETERMINATION

Power for Aim 1:

Sample size for the study is based primarily on Aim 1, although we also provide effect size (ES) estimates for the other aims given the proposed sample size. With respect to Aim 1, with a total sample of 480, the approach provided by Crivello and colleagues^{178,179,180} guarantees that the adaptive intervention with the lowest estimated mean suicide risk (ideation + behaviors) at post-treatment is, in fact, the best adaptive intervention with 90% probability. This calculation assumes that the best two ATSSs differ by $d = 0.25$ (or ≥ 2 points on the SSI), which corresponds to a small ES estimate.¹⁸¹

Power for Aim 2:

Aim 2 is a two-sample comparison (cells A+B+C vs. D+E+F). Using a two-side, two-sample t-test based on Type-I error rate of 2.5%, a sample of 240 randomized to each Stage 1 treatment arm (N=480 total), we will have 85% power to detect a small, standardized ES of $d = 0.30$ in the between groups difference in change on the primary outcomes. Based on prior studies and our pilot data with $SD=7$ for SSI,¹¹³ this ES corresponds to a clinically meaningful difference of 2 in the SSI. Note that this is a conservative estimate of power: in the repeated measures LMM, power increases in proportion to the within person correlation in baseline to 26-week SSI which can be as high as 0.40 ($p < .01$, based on pilot data). At 3-month follow-up (assuming a baseline to 48-week within correlation of 0.3) we will have 94% power to detect the same moderate ES.

Power for Aim 3:

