Aim 2 analyses will contrast ATSSs beginning with CAMS vs. interventions beginning with TAU (i.e., to evaluate the main effect of initial treatment) on change (decrease) in suicide-related risk behaviors (SI, NSSI, and suicide attempts—the primary outcomes) from baseline to the end of Stage 2 (the primary contrast). This is a comparison of cells A+B+C vs. D+E+F (see Figure 2 and Table 8). Note that the primary continuous longitudinal outcome is assessed at baseline, mid-Stage 1 (3 weeks), post Stage 1 (6 weeks), mid-Stage 2 (10 weeks), post-Stage 2 (14 weeks) (end of acute treatment) and then again at 3-month follow-up (26 weeks), for a total of 6 measurement occasions. Linear mixed models¹⁶³ (LMM, also known as random effects or growth curve models), fit with SAS PROC MIXED will be used to analyze the longitudinal data. LMMs use all available measurements, allowing student participants to have an unequal number of observations and producing unbiased parameter estimates as long as unobserved values are missing at random. The analysis will fit a LMM with fixed effects for the intercept, time, group, and a group-by-time interaction term, where group is an indicator of phase-one treatment (CAMS vs. TAU as referent). The LMM will also include random effects for the intercept and time and an unstructured within-person correlation structure for the residual errors and will adjust for the following measures collected at baseline (pre-randomization): site, age, race, and clinical severity. Model diagnostics will be used to determine suitability of more parsimonious (e.g., autoregressive) correlation structures, and nonlinear (e.g., quadratic) effects for time. We do not expect the intervention effects to be attenuated due to counselor participants who are cross classified between the interventions. Nonetheless, we will assess the potential attenuation by assessing the counselor x intervention interaction. If significant, we will examine if the attenuation effect is limited to a select few counselors and eliminate as needed to remove potential counselor contamination of intervention effects. Counselor will be treated as a random effect which models potential correlation between student participants within a common counselor. If there is not sufficient variance, indicated by the reliability estimate of the random effect falling below 0.02 (a slighter lower threshold compared to

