Raudenbush and Bryk¹⁶⁴ (p.125), we will treat counselor as a fixed effect. The primary contrast is between groups' difference in change from baseline to month 6 (end of acute treatment through Stage 1 and Stage 2 active treatment). The follow-up contrast at week 26 (12 weeks post-acute treatment) will also be examined in this and in all subsequent analyses. LMMs like the above for the primary outcome will be run for the secondary longitudinal outcomes: CAMS vs. TAU on CCAPS subscales (Depression, Anxiety, Academic Distress, Overall Distress), CGI-I and CGI-S (measured by IE), and cumulative GPA.

AIM 3 analyses will examine the relative effectiveness of switching to a more comprehensive suicide-focused treatment approach (e.g., CC-DBT) among those who do not respond sufficiently to Stage 1 treatments vs. a less intensive suicide-focused approach (e.g., CAMS). This analysis is a comparison of cells C+F (switch to CC-DBT) vs. B+E (switch or continue with CAMS) in Table 8. Both primary and secondary longitudinal outcomes outlined above will be examined using an LMM like that described above, but (a) including only the subset of responders to Phase 1 treatment, (b) defining group as switching to CC-DBT (cells C+F) vs. continuing or switching to CAMS (cells B+E), and (c) using monthly longitudinal outcomes from week 4 to week 24 (7 measurement occasions).

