Aim 8 analyses focus on statistical contrast of the two randomized arms within Stage 1 and the two randomized arms within Stage 2. For Stage 1 comparisons, linear mixed models¹⁶³ (LMM, also known as random effects or growth curve models), fit with SAS PROC MIXED will be used to analyze the longitudinal data. LMMs use all available measurements, allowing student participants to have an unequal number of observations and producing unbiased parameter estimates if unobserved values are missing at random. The analysis will fit a LMM with fixed effects for the intercept, time, group, and a group-by-time interaction term, where group is an indicator of stage-one treatment (CAMS vs. TAU as referent). The LMM will also include random effects for the intercept and time and an unstructured within-person correlation structure for the residual errors and will adjust for the following measures collected at baseline (pre-randomization): site, age, race, and clinical severity. Model diagnostics will be used to determine suitability of more parsimonious (e.g., autoregressive) correlation structures, and nonlinear (e.g., quadratic) effects for time. Complexity of the model may be constrained by the available repeated measures. Counselor will be treated as a random effect which models potential correlation between student participants within a common counselor. If there is not sufficient variance, indicated by the reliability estimate of the random effect falling below 0.02 (a slighter lower threshold compared to Raudenbush and Bryk¹⁶⁴ (p.125), we will treat counselor as a fixed effect. The primary contrast is between groups’ difference in change from baseline to end of Stage 1. Comparison of these findings will be to the results from the linear contrasts of the components of the ATS as described in Aim 1.

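### The Aim 2 and Aim 8 Stage 1 mixed models leave the randomised arms' baseline means free; a common baseline mean would give a more precise change contrast at no cost, by an amount the documents do not fix

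*Combined protocol and SAP*

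**What the plan says.** Section 9.3.2 (Aim 2) counts baseline among six measurement occasions of the outcome and describes a growth-curve mixed model: "The analysis will fit a LMM with fixed effects for the intercept, time, group, and a group-by-time interaction term". It adds random effects for intercept and time, and leaves non-linear time to model diagnostics. The model "will adjust for the following measures collected at baseline (pre-randomization): site, age, race, and clinical severity". The primary contrast is the between-group "difference in change from baseline to month 6". I read this as week 14, because the same sentence equates it with the end of acute treatment and the section puts the end of Stage 2 at 14 weeks.

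Section 9.3.7 (Aim 8, Stage 1) repeats the model, with the contrast taken as the "difference in change from baseline to end of Stage 1".

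Section 6.1.4 places randomisation after baseline: "Following the completion of the baseline assessment". Section 9.2 (Power for Aim 2) calls its t-test power conservative because mixed-model power rises with the "within person correlation in baseline to 26-week SSI which can be as high as 0.40".

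Neither model lists an equal-baseline constraint, baseline SSI as a named covariate, or covariate-by-time terms. Clinical severity is not defined.

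**The concern.** Because baseline is measured before assignment, the arms have the same expected baseline mean. A free group main effect estimates a quantity known to be zero, and the change contrast then subtracts that estimate in full. This removes no bias and adds noise. When the baseline correlation is below 0.5, a simple change from baseline is noisier than the follow-up score alone.

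The covariate list does not compensate. With the terms as listed and complete data, a covariate that is constant over time and enters as a main effect shifts every occasion equally, so it cancels from within-person change. What is at stake is precision in the test of a suicide-focused against a usual-care first-line treatment, and whether the adjustment set sharpens the contrast it accompanies.

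**Working it through.** **Inputs.** From 9.2, Power for Aim 2: 240 per arm, two-sided 2.5%, d = 0.30, SD 7 for SSI, correlation up to 0.40 (baseline to week 26) and 0.30 (follow-up). From 9.2, Power for Aim 3: correlation 0.60. From 4.2: pilot attrition 27% and 17%. Assumed: equal variances over time, SSI SD scaled to 1, and 25% missing where stated.

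**The plan's own figure.** SE = √(2/240) = 0.0913. Power = Φ(0.30/0.0913 − 2.241) = Φ(1.045) = 85.2%. The stated 85% is reproduced.

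**Visit-specific means, complete data.** The contrast variance is a factor times 2/240:
- free baseline means: 2(1 − r)
- common baseline mean: 1 − r²
- proportional cut: 1 − (1 + r)/2 = (1 − r)/2

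| r | free | common | cut |
|---|---|---|---|
| 0.30 | 1.40 | 0.91 | 35% |
| 0.40 | 1.20 | 0.84 | 30% |
| 0.60 | 0.80 | 0.64 | 20% |

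Power at r = 0.40 with d on the cross-sectional SD:
- free: variance 1.20 × 2/240 = 0.0100, power Φ(3.000 − 2.241) = 77.6%
- common: variance 0.84 × 2/240 = 0.0070, power Φ(3.586 − 2.241) = 91.1%

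**Dropout.** With a fraction f missing at follow-up, the factors are (1 − r²)/(1 − f) + (1 − r)² (free) and (1 − r²)/(1 − f) (common). At r = 0.40 and f = 0.25 they are 1.12 + 0.36 = 1.48 and 1.12, a cut of 24%. Completers' change alone gives 1.20/0.75 = 1.60, so with dropout the planned model does recover some baseline information.

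**Linear time, weeks 0, 3, 6, 10, 14, 26, change to week 14.** With equal correlation 0.40:
- free: the sum of squares of the weeks about their mean is 1017 − 59²/6 = 436.8, so the factor is 196 × 0.6/436.8 = 0.269
- common: the information is [1017 − (0.4/3.0) × 59²]/0.6 = 921.4, so the factor is 196/921.4 = 0.213
- cut: 21%

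Other assumed covariances:
- equal correlation 0.60: cut 12%
- correlation decaying to 0.40 at week 26: 0.348 against 0.242, cut 30%
- correlation decaying to 0.40 at week 14: 0.473 against 0.272, cut about 42%
- some random-intercept-and-slope patterns: ratios 1.07 to 1.13, cuts of about 7–12%

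If the effect is truly linear, power for d = 0.30 was at least 97% under either model across the patterns tried. For instance, the factor 0.473 gives SE √(0.473 × 2/240) = 0.0628 and power Φ(4.78 − 2.24) = 99%.

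**Aim 8 Stage 1.** No baseline to week 6 correlation is given. If correlation decays to 0.40 at week 26, the week 6 value is 0.40^(6/26) = 0.81 and the cut is (1 − 0.81)/2, about 10%. Equal correlation 0.30 with linear time over weeks 0, 3 and 6 gives about 40%. The documents do not choose between these.

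**Covariates.** Suppose a covariate correlates c with SSI at both visits. The free-baseline factor after adjustment is 2[(1 − c²) − (r − c²)] = 2(1 − r), so it is unchanged. In simulated complete data with two and five occasions, the contrast with and without the main effect agreed to within 1e-15. With a common baseline the factor becomes (1 − c²) − (r − c²)²/(1 − c²). At r = 0.40 this is 0.836 for c = 0.1 and 0.804 for c = 0.3, against 0.84 unadjusted: 0.4% to 4% less variance.

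**The case against.** The planned model is conventional and valid. Aim 2 is secondary, Aim 8 exploratory, and the primary Aim 1 uses a separate weighted comparison that is untouched. The natural reading of 9.3.2 is continuous time, where the contrast is a slope over six occasions rather than a raw difference in change. If the effect is truly linear, power is high with either model. All of this stands.

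A reader might infer several stronger things that the documents do not support:
- **That about 30% of precision is lost, full stop.** The 0.40 is an upper value for baseline to week 26. No week 14 or week 6 correlation is given, and decay to 0.40 at week 26 would put the visit-specific week 14 cut nearer 20%.
- **That the size does not depend on how time is coded.** It does, and the effect on power depends on it more.
- **That Aim 2 really has 78% power.** That needs visit-specific means, r = 0.40, and d scaled to the cross-sectional SD of 7. Section 9.2 words the effect as a difference in change; if d is scaled to the SD of change, the stated 85% stands.
- **That baseline and covariates contribute nothing.** This is exact only for complete data. Main effects only is an inference from the listed terms, and 9.3.1 leaves covariate entry partly open.

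None of this supplies a reason to prefer free baseline means in a trial randomised after baseline.

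**Conclusion.** The point holds as an efficiency matter and is a free improvement; it is not an error that biases a result. With visit-specific means and complete data, the contrast variance could be cut by 35%, 30% or 20% at the documents' correlations of 0.30, 0.40 and 0.60, and by less with dropout. With linear time the range is roughly 7–42%; it rests on assumed covariances and illustrates the spread rather than bounding it. For Aim 8 Stage 1 the direction is clear and the size is not established.

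The power comparison of 78% against 91% holds only under the three conditions named above. Under visit-specific means with d on the cross-sectional SD, the claim in 9.2 that the t-test figure is conservative needs 2(1 − r) below 1, that is r above 0.5; with a common baseline mean it holds at 0.40.

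**What to change.** In 9.3.2 (Aim 2) and 9.3.7 (Aim 8 Stage 1), specify one of these:
- Constrain both arms to a common baseline mean: drop the group main effect at time 0, with time coded from baseline, and keep the group-by-time terms. Randomised participants with only a baseline value stay in the likelihood.
- Model post-baseline SSI only, with baseline SSI and baseline SSI-by-visit as covariates.

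Also state whether time is linear or by visit, whether covariate-by-time terms are included, and what clinical severity is. If it means baseline SSI, it cannot be both a response and a covariate. Under either form the listed covariates can contribute, probably modestly.

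The core change costs a sentence in each section and a small change to the PROC MIXED code, with no new data. It should be fixed before unblinded analysis.

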Notes (2): \$For all assessments collected as part of an Independent Evaluator (IE) visit (i.e., those assessments not collected specifically at treatment visits), there will be a +/-1 week window around the scheduled assessment date for purposes of data collection. IE assessments collected outside of this window will still be collected and values will be imputed based on when the assessment should have occurred.																
Notes (3): *These measures are exclusively collected in the Titanium electronic medical record and will be exported at regular intervals throughout the study period.																

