4.2 OVERALL DESIGN

As shown in Figure 1 (on page 9), the proposed multisite SMART will involve randomization at two stages. At Stage 1, all student participants ($N = 480$) will be randomized to 4-6 weeks of CAMS or TAU. Beginning at session 4, the counselor will rate the student participant in terms of clinical response. Insufficient responders (e.g., non-responders) to Stage 1 will be re-randomized to one of two Stage 2 treatments for an additional 1-8 weeks: 1) CAMS (either continued or for the first time) or 2) CC-DBT.

Thus, four ATSSs are possible:

- ATS-1: Start with CAMS, if responding, enter maintenance treatment; if not, continue with CAMS;
- ATS-2: Start with CAMS, if responding, enter maintenance treatment; if not, switch to CC-DBT;
- ATS-3: Start with TAU, if responding, enter maintenance treatment; if not, switch to CAMS;
- ATS-4: Start with TAU, if responding, enter maintenance treatment; if not, switch to CC-DBT.

Our pilot showed at Stage 1, 48% and 44% treatment response rates across CAMS and TAU, with 27% and 17% attrition rates, respectively—differences not statistically significant. Based on these findings, we assume an equal response rate of 50% across both Stage 1 treatments (CAMS and TAU), leaving $N=240$ participants eligible for Stage 2 treatments. Treatment responders at the end of Stage 1 will end study treatment and enter maintenance, which includes monthly monitoring and continued assessments with the IEs. All student participants will complete weekly measures as part of treatment. Research assessments by independent evaluators (IEs) will be conducted at baseline, mid-Stage 1 (Week 3), end of Stage 1 (Week 6), mid-Stage 2 (Week 10), end of Stage 2 (Week 14), and at 3-month follow-up (Week 26).

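### The mixed model for Aims 2, 3 and 8 has three more covariance parameters than the data can identify, and the covariance and time form are left to diagnostics.

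*Combined protocol and SAP*

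**What the plan says.** Section 9.3.2 sets out the longitudinal model under Aim 2. It is to be "fit with SAS PROC MIXED will be used to analyze the longitudinal data", with "fixed effects for the intercept, time, group, and a group-by-time interaction term". On covariance: "The LMM will also include random effects for the intercept and time and an unstructured within-person correlation structure for the residual errors". Counselor is listed separately as a further random effect, so the intercept and time effects read as student-level.

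The outcome is taken at weeks 0, 3, 6, 10, 14 and 26, "for a total of 6 measurement occasions"; Section 4.2 gives the same evaluator schedule. For evaluator assessments outside the one-week window, the notes to Table 1 (Section 1.3) say that "values will be imputed based on when the assessment should have occurred".

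The same section then allows for change: "Model diagnostics will be used to determine suitability of more parsimonious (e.g., autoregressive) correlation structures". That sentence goes on to allow nonlinear time, with a quadratic as its example.

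Aim 3 uses a model like the Aim 2 one, and so do the secondary longitudinal outcomes. Section 9.3.7 repeats the covariance wording for both stages of Aim 8: "random effects for the intercept and time and an unstructured within-person correlation structure for the residual errors". It adds that the number of repeated measures may limit how complex the model can be; for Stage 2 this remark also names the variance and covariance structures.

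**The concern.** An unstructured residual matrix gives every visit its own variance and every pair of visits its own covariance. When all students share the same nominal visit times, a random intercept and slope contribute a covariance pattern that this matrix can already reproduce exactly. The two components then compete for the same information, and only their sum is determined by the data.

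Someone programming the model must drop or restrict one of them, and the plan gives no rule for this. The same paragraph leaves the residual structure and the form of time to diagnostics. The time form carries more weight, because the base model has a single linear group-by-time term over 26 weeks while the main contrast is baseline to the end of Stage 2. A straight line and a curve can give very different values at week 14. The issue is whether the Aim 2 estimate is fixed before outcome data are examined.

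**Working it through.** **1. Inputs.**
- Visits: weeks 0, 3, 6, 10, 14, 26 for Aim 2 (Sections 4.2 and 9.3.2).
- Aim 3: seven occasions, as Section 9.3.2 states. The Section 4.2 schedule would give four from week 6 onward (6, 10, 14, 26).
- Aim 8: three evaluator visits per stage, weeks 0, 3, 6 and about weeks 6, 10, 14.
- Random intercept and slope: 3 parameters (two variances and a covariance), written G.
- Unstructured residual matrix over k visits, written R: k(k+1)/2 parameters.

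**2. Parameter count.** The data supply k(k+1)/2 distinct variances and covariances. The model uses 3 + k(k+1)/2. The number identifiable is the rank of the derivative of the marginal covariance ZGZ' + R with respect to all its parameters, computed numerically.

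| Analysis | k | Parameters | Rank |
|---|---|---|---|
| Aim 2 | 6 | 3 + 21 = 24 | 21 |
| Aim 3, occasions as stated | 7 | 3 + 28 = 31 | 28 |
| Aim 3, Section 4.2 schedule | 4 | 3 + 10 = 13 | 10 |
| Aim 8, each stage | 3 | 3 + 6 = 9 | 6 |

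The excess is three in every row.

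**3. Other readings.** If the text means one common variance with an unstructured correlation matrix, Aim 2 has 3 + 1 + 15 = 19 parameters with rank 18, and Aim 8 has 3 + 1 + 3 = 7 with rank 6, so one is still redundant. If actual visit times, varying by up to a week, were used instead of nominal ones, the intercept variance would remain unidentified. The slope variance would be very poorly determined: a standard error of about 5.8 for a true value of 4, with illustrative variances.

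**4. Effect on the treatment contrast.** One data set was simulated with 480 students, six visits and illustrative variances. Four choices of G, including G = 0, were each paired with the R that keeps the total covariance the same. All gave log-likelihood -9237.02, group-by-time estimate -1.091 and standard error 0.296, identical to unstructured R alone. The redundancy by itself therefore moves neither the estimate nor its standard error.

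**5. Effect of the time form.** Assume, since the documents give no trajectory, group differences of 0, 1, 2, 2, 2, 2 at the six visits. Two points is the difference that Section 9.2 calls clinically meaningful.

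- Mean week = 59/6 = 9.833; mean difference = 9/6 = 1.5.
- Sxy = 115 - 6 × 9.833 × 1.5 = 26.5.
- Sxx = 1017 - 6 × 9.833² = 436.8.
- Linear slope = 26.5/436.8 = 0.0607 per week, so the week-14 contrast is 0.0607 × 14 = **0.85**.
- Quadratic fit: 0.24925 × 14 - 0.007125 × 14² = 3.490 - 1.397 = **2.09**, against an assumed truth of 2.0.

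The 0.85 also holds under a random intercept and slope with independent residuals. Because the straight line is wrong for this pattern, the covariance choice also shifts the linear estimate. By generalised least squares it is 0.66 to 0.77 with AR(1) by visit (correlation 0.7 to 0.4) and 0.98 to 1.06 with AR(1) by week (0.90 to 0.97). The quadratic stays above 2 under the same structures.

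**6. Identified alternatives.** Unstructured R without student random effects: 21 of 21 at six visits, 6 of 6 at three. Random intercept and slope with AR(1) residuals: 5 parameters, rank 5, at 3, 4, 6 and 7 visits.

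**7. Side check.** Two-sample power with 240 per arm, d = 0.30 and two-sided alpha 2.5% is 85.2%, matching the stated 85%. It does not involve the mixed model.

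**The case against.** A reader might infer that the model cannot be fitted, that the software will fail to converge, or that the reported standard errors depend on how the redundancy is resolved. None of these is supported. Step 4 shows the same contrast and standard error for every G tried. If the software set G to zero, the result would be the unstructured-only covariance recommended below. Hessian or G-matrix warnings, or an arbitrary G, are possible; PROC MIXED was not run, so nothing firmer can be said.

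The plan also foresees simplification. It names autoregressive structures, and a random intercept and slope with AR(1) residuals is identified. For Aim 8 it says that few repeated measures may restrict the model, which covers the three-visit case in general terms. It allows quadratic time, so 0.85 would be the final answer only if an evidently curved trend were left as a line. A growth curve is a legitimate choice, and the covariance redundancy and the time form are separate matters. The reach is limited too: Section 9.3.1 makes Aim 1 primary and Aim 2 secondary, and Aim 8 is exploratory.

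All of that stands. What it does not supply is a rule. The plan does not recognise its starting model as redundant, does not say which component to drop, gives no criterion or order for the alternatives, and leaves the shape of time to be settled from the outcome data.

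**Conclusion.** The specification is wrong as written, with moderate consequences. The covariance model exceeds what can be identified by three parameters at every stated number of visits. This makes the split between random effects and residuals arbitrary, while the marginal covariance and the contrasts for CAMS against TAU and CC-DBT against CAMS remain estimable.

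The larger practical consequence is the deferred time form. On the assumed early-benefit pattern the Aim 2 contrast at week 14 is about 0.85 under the base model and about 2.1 under the permitted quadratic. These figures illustrate dependence on an open choice; they do not predict bias in the final analysis.

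The conclusion assumes student-level random effects and nominal visit times. It also takes the main contrast at week 14, the end of Stage 2, although a later sentence in Section 9.3.2 calls the same contrast month 6. At week 26 the assumed pattern gives 0.0607 × 26 = 1.58 with linear time and 0.24925 × 26 - 0.007125 × 26² = 1.66 with quadratic time, so the two forms would nearly agree there.

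Aim 1 uses a weighted comparison and is untouched, as is the Aim 2 power figure.

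**What to change.** For Aims 2, 3 and 8, and for the secondary outcomes that reuse the model, the SAP should state:

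- visit as a categorical factor with group-by-visit terms, so that the week-14 difference in change from baseline is estimated directly;
- one unstructured within-student covariance, with no student random intercept or slope;
- the counselor random effect kept as planned;
- an ordered fallback used only on non-convergence, for example heterogeneous Toeplitz and then AR(1). The SAP should say whether lag counts visits or weeks, since the gaps between visits run from 3 to 12 weeks.

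If the team prefers a growth curve, an identified alternative is a random intercept and slope with one named simple residual structure. The time form would then also have to be fixed before outcome data are examined.

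The change is to SAP wording only, with no new data, visits or participants. Categorical visit uses 6 × 2 = 12 fixed effects for visit and group in place of 4 at six visits (8 more), and 3 × 2 = 6 in place of 4 at three visits (2 more). With 480 students in Aim 2 that is a small price.
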